4 ELIGIBILITY CRITERIA

The following eligibility criteria are designed to select subjects for whom protocol treatment is considered appropriate. All relevant medical and non-medical conditions should be taken into consideration when deciding whether this protocol is suitable for a particular subject.

4.1 Inclusion

1. Patients must be refractory to, or not a candidate for, established therapy known to provide clinical benefit for their malignancy.
2. Measurable disease M protein component in serum (at least 0.5 g/dL) and/or urine (if present) (≥ 0.2 g excreted in a 24 hour collection sample), or serum free light chain level ≥ 10 mg/dL, provided the serum free light chain ratio was abnormal.
3. Able to swallow and retain oral medication.
4. All previous therapies for cancer, including radiotherapy, major surgery and investigational therapies must be discontinued for ≥ 14 days (≥ 28 days for mitomycin C or nitrosoureas) before study entry, and all acute effects of any prior therapy must have resolved to baseline severity or Grade ≤ 1 Common Terminology Criteria for Adverse Events (CTCAE v4.03), except alopecia or parameters defined in this eligibility list.
5. Age ≥ 18 years
6. ECOG performance status ≤ 1
7. Adequate organ and marrow function as defined below:
 - h. Absolute neutrophil count $\geq 1,000/\text{mm}^3$ without growth factor use ≤ 7 days prior to treatment (cycle 1 day 1, C1D1)
 - i. Platelets $\geq 50,000/\text{mm}^3$ without platelet transfusion ≤ 3 days prior to C1D1
 - j. Hemoglobin ≥ 8.0 mg/dL without red blood cell transfusion ≤ 3 days prior to C1D1
 - k. Total serum bilirubin $\leq 1.5 \times$ upper limit of normal (ULN) ; subjects with $>1.5 \times$ upper limit of normal require approval of medical monitor.
 - l. AST (SGOT)/ALT (SGPT) $\leq 2 \times$ ULN; $\leq 5 \times$ ULN if liver dysfunction is felt to be secondary to tumor burden
 - m. Serum creatinine $\leq 1.5 \times$ ULN (OR creatinine clearance ≥ 30 mL/min/1.73 m²)
 - n. Serum or urine pregnancy test (for females of childbearing potential) negative ≤ 7 days of starting treatment
8. Ability to understand and the willingness to sign a written informed consent document and comply with the study scheduled visits, treatment plans, laboratory tests and other procedures.
9. Female patients must be surgically sterile or be postmenopausal, or must agree to use effective contraception during the period of the trial and for at least 90 days after completion of treatment. Male patients must be surgically sterile or must agree to use effective contraception during the period of the trial and for at least 90 days after completion of treatment. The decision of effective contraception will be based on the judgment of the principal investigator or a designated associate.

CONFIDENTIAL

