- Assess effect of ONC201 in combination with dexamethasone on survival endpoints.

Primary Endpoint

- Overall response rate (ORR) using the International Myeloma Working Group response criteria.

Secondary Endpoints

- Overall safety profile of ONC201 as characterized by type, frequency, severity, timing and relationship to study therapy of adverse events and laboratory abnormalities.
- Effects of ONC201 on pharmacodynamic (PD) markers.
- Effects of ONC201 on survival endpoints (i.e., progression-free survival, time to progression, and duration of response).

Study design

This is a Phase 1/2 open-label study of ONC201 administered orally once every week in combination with dexamethasone to patients with relapsed/refractory multiple myeloma.

In Phase 1 of the study, patients will receive 625 mg ONC201 once every week in combination with dexamethasone using a 3+3 dose escalation design that will evaluate up to 625mg ONC201 weekly with 20mg dexamethasone. Three weeks is defined as a treatment cycle.

Phase 1 of the study will involve a safety cohort of at least 6 relapsed/refractory multiple myeloma patients who will receive ONC201 and dexamethasone.

In Phase 2 of the study, patients will receive 625mg ONC201 once every week. Dexamethasone will be administered at a dose determined in Phase 1. Patients may not cross over from Phase 1. Tumor assessments will be conducted using the International Myeloma Working Group response criteria. The study plans to enroll 42 patients over a period of 2 years.

Eligibility criteria

Inclusion

1. Patients must be refractory to, or not a candidate for, established therapy known to provide clinical benefit for their malignancy.
2. Measurable disease M protein component in serum (at least 0.5 g/dL) and/or urine (if present) (≥ 0.2 g excreted in a 24 hour collection sample), or serum free light chain level ≥ 10 mg/dL, provided the serum free light chain ratio was abnormal.
3. Able to swallow and retain oral medication.
4. All previous therapies for cancer, including radiotherapy, major surgery and investigational therapies discontinued for ≥ 14 days (≥ 28 days for mitomycin C or nitrosoureas) before study entry, and all acute effects of any prior therapy resolved to baseline severity or Grade ≤ 1 Common Terminology Criteria for Adverse Events (CTCAE v4.03), except alopecia or parameters defined in this eligibility list.
5. Age ≥ 18 years.
6. ECOG performance status ≤ 1 .

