1.1 Proposed Indication

ONC201 is intended for treatment of adult patients with relapsed/refractory multiple myeloma for whom no standard therapy is available.

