Another arm of this study has been opened to evaluate weekly dosing. Three patients have been treated with 375mg ONC201 on a weekly basis and six patients have been treated with 625mg on a weekly basis. As of September 8, 2016, there have been no reports of drug-related adverse events in any of these patients. All three 375mg and six of the 625mg patients have successfully completed the DLT window (21 days). Based on these findings, the recommended administration schedule of ONC201 is 625mg once every week.

Additional clinical studies of ONC201 are enrolling, including a Phase I clinical trial in advanced solid tumors and multiple myeloma, a Phase I/II clinical trial in relapsed/refractory acute leukemias and high-risk myelodysplastic syndrome (MDS), a Phase I/II clinical trial in relapsed/refractory Non-Hodgkin's lymphoma (NHL) and a Phase II clinical trial in bevacizumab-naïve glioblastoma multiforme (GBM).

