3.2 Number of Patients

Phase 1 is expected to enroll up to 12 patients and Phase 2 will enroll up to 30 evaluable patients over the course of 2 years. The actual sample size will depend on the clinical results.

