8.2 Efficacy Evaluations

Assessment of response will be made using the International Myeloma Working Group response criteria (Palumbo et al, 2014). All patients' files and radiologic images must be available for source verification.

Imaging may include chest, abdomen and pelvis CT or MRI or PET/CT scans (when applicable); brain CT or MRI scan for patients with known CNS involvement; bone scan and/or bone x-rays for patients with lytic bone lesions, if applicable.

Tumor assessments conducted at baseline, at the end of every other cycle, whenever disease progression is suspected (e.g., symptomatic deterioration), and at the time of withdrawal from the study (if not done in the previous 6 weeks).

The same imaging technique used to characterize each identified and reported lesion at baseline will be employed in the following tumor assessments.

Assuming a background ORR of 10%, if the ORR on the current study for patients receiving ONC201 were 30% or higher there would be interest in further investigation of this treatment regimen. Therefore, this study will be used to detect a difference of 20% using a one- sided binomial test. Statistically, the hypothesis that will be tested is:

$H_0: p \leq 0.1$ versus $H_1: p > 0.3$

where p is the proportion of patients achieving an objective response. Enrollment of 30 patients will yield 84% power to detect a 20% difference at an alpha level of 0.05 (one-sided).

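### The numbered eligibility criteria do not carry the protocol's own stated population and do not exclude prior ONC201, while the single-arm ORR test is sensitive to case mix

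*Combined protocol and SAP*

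**What the plan says.** **Population.** Section 1.1 gives the indication as adults with "relapsed/refractory multiple myeloma for whom no standard therapy is available". The title, synopsis, introduction and Section 3.1 also describe the disease as relapsed/refractory.

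**Criteria.** In Section 4.1 and the synopsis, inclusion 1 is the only numbered criterion on treatment history: "Patients must be refractory to, or not a candidate for, established therapy known to provide clinical benefit for their malignancy". No criterion mentions relapse, a number of prior lines, or earlier dexamethasone. Inclusion 4 accepts earlier investigational therapy that ended at least 14 days before entry. Exclusion 3 bars only patients being treated in another study at the time. Neither list names prior ONC201.

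**Re-exposure.** The synopsis study design says "Patients may not cross over from Phase 1"; Sections 3 and 4 do not repeat it. Section 1.3 lists, among ONC201 trials then enrolling, "a Phase I clinical trial in advanced solid tumors and multiple myeloma".

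**Test.** Section 8.2 begins "Assuming a background ORR of 10%, if the ORR on the current study for patients receiving ONC201 were 30% or higher" and continues that "this study will be used to detect a difference of 20% using a one- sided binomial test". It claims 84% power with 30 patients at one-sided alpha 0.05. It gives neither a source for the 10% nor the population or regimen that it describes. All patients receive dexamethasone (Section 6.1.2), supplied and given according to usual myeloma care (Section 5.2).

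**The concern.** With no control arm, ORR says something about ONC201 only if the 10% is close to the rate these same patients would show without ONC201 activity. Who is admitted largely decides that, so the criteria should fix the population. As written they leave two gaps.

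First, the stated population is in the descriptive text but not in the list that a site checks at enrolment. The response rate to expect without ONC201 activity therefore depends partly on how each site reads inclusion 1. Dexamethasone makes this matter, because it is a myeloma treatment in its own right.

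Second, a patient whose disease progressed on ONC201 in another trial can meet every numbered criterion. Such patients would probably lower the observed ORR, and in Phase 1 they would be counted in the DLT cohorts without being ONC201-naive. The sponsor evidently saw a reason to keep Phase 1 patients out of Phase 2; the same reasoning applies to ONC201 exposure in other trials.

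**Working it through.** **1. Inputs.** From Section 8.2: n = 30, p0 = 0.10, p1 = 0.30, one-sided alpha 0.05. From Section 3.2: "Phase 2 will enroll up to 30 evaluable patients over the course of 2 years". The documents give neither the share of ONC201-pretreated patients, nor their response rate, nor the response rate on dexamethasone alone. Those are assumptions below, shown as ranges.

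**2. The plan's own figure.** Let X be the number of responders, X ~ Bin(30, p). The cut-off is the smallest r with P(X ≥ r | 0.10) ≤ 0.05.

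- r = 6: P(X ≥ 6 | 0.10) = 0.073, too high.
- r = 7: P(X ≥ 7 | 0.10) = 0.0258, and power is P(X ≥ 7 | 0.30) = 0.8405.

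The stated 84% is reproduced. The arithmetic is sound, so the question is whether 10% applies to the patients admitted. (The futility table in Section 10.2 stops at 26 patients. At n = 26 the cut-off is 6, with alpha 0.040 and power 0.837, so the design is similar. The mismatch between 26 and 30 is a separate matter.)

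**3. Sensitivity to the background rate.** Keep the cut-off at 7 of 30, suppose ONC201 adds nothing, and let the true rate be b. The false-positive rate is P(X ≥ 7 | b).

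| True rate b without ONC201 activity | False-positive rate |
|---|---|
| 10% | 0.026 |
| 11.5% | 0.050 |
| 12% | 0.061 |
| 15% | 0.153 |
| 20% | 0.393 |

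The nominal 0.05 is used up at about 11.5%, a drift of 1.5 percentage points. The values of b are assumptions; the documents do not show which applies.

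**4. Sensitivity to prior ONC201.** Let a share s be ONC201-pretreated with response rate q, and let the rest respond at 30%. The blended rate is 0.30(1 − s) + q·s. Examples:

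- s = 0.10, q = 0.10: 0.27 + 0.01 = 0.28.
- s = 0.20, q = 0.10: 0.24 + 0.02 = 0.26.

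Power is P(X ≥ 7 | blended rate).

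| Share s (assumed) | q = 10%: rate, power | q = 0%: rate, power |
|---|---|---|
| 0% | 30%, 0.84 | 30%, 0.84 |
| 10% | 28%, 0.78 | 27%, 0.74 |
| 20% | 26%, 0.70 | 24%, 0.60 |

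The q = 10% column is consistent with the plan's own background, since these patients also receive dexamethasone. The q = 0% column is the pessimistic end.

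**5. Does another criterion close the gap?** Exclusion 10 covers severe conditions or laboratory abnormalities that could interfere with interpretation, with investigator judgement. It names neither prior ONC201 nor prior dexamethasone. The 14-day washout in inclusion 4 deals with timing, not with resistance. The remaining exclusions concern comorbidity, infection, disease form, pregnancy, concurrent trials and interacting drugs.

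**The case against.** The strongest reply is that inclusion 1, read naturally, means that no useful established treatment remains, which is the Section 1.1 population. If dexamethasone counts as established therapy, the criterion arguably already keeps out patients still sensitive to it. Much of this stands. The wording does not settle whether being refractory to one established therapy is enough, and the documents do not show that dexamethasone-sensitive patients would be enrolled.

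A reader might go further and infer three things that the documents do not support.

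- *The criteria mismatch the population behind the 10%.* Section 8.2 defines no such population. The 10% may already be a rate on dexamethasone in a mixed population, and adding a dexamethasone effect on top would then count it twice.
- *Untreated patients are eligible.* The branch for patients who are not candidates for established therapy requires no earlier treatment. But enrolling an untreated patient would contradict the title, the indication and Section 3.1. What is missing is the matching criterion.
- *The false-positive rate is inflated by a known amount.* Any such figure depends on an assumed share of dexamethasone-sensitive patients and an assumed response rate in them, and the protocol gives neither.

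On prior ONC201, it is fair to say that Section 1.3 shows a possible route, not that anyone would take it, and that the synopsis already bars Phase 1 patients from Phase 2. Neither point closes the gap for patients from other ONC201 trials.

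**Conclusion.** The concern holds in a limited form. The numbered criteria do not carry the protocol's stated population, and they allow ONC201-pretreated patients into the Phase 1 DLT cohorts and into the single-arm ORR test. The plan's power figure is correct.

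The size is conditional. The false-positive rate exceeds 0.05 once the true rate without ONC201 activity passes about 11.5%; whether it does cannot be determined from the documents. With assumed shares of 10% and 20% ONC201-pretreated patients, power falls from 0.84 to 0.78 and 0.70 if they respond at 10%, or to 0.74 and 0.60 if none respond. Quoting only the last pair would overstate the loss unless the zero response rate is stated as an assumption.

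A higher background rate and prior ONC201 exposure push ORR in opposite directions. Nothing makes them cancel, and the net direction is unknown. This should be corrected because it bears on how the primary endpoint is read, but it is not evidence that the 10% is wrong or that the test fails.

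**What to change.** 1. In inclusion 1 (Section 4.1 and synopsis), require the Section 1.1 population: "relapsed/refractory multiple myeloma for whom no standard therapy is available".
2. In the exclusions (Section 4.2 and synopsis), add prior treatment with ONC201, in this or any other study. This also brings the no-crossover rule into the criteria.
3. Record prior dexamethasone exposure and refractoriness with the tumor history already taken at baseline (Section 7.1). In Section 10.1, add a descriptive table of ORR with exact confidence intervals by that status, and state that it supports interpretation and does not correct the pooled primary test.
4. In Section 8.2, state which population and which regimen the 10% refers to, and its source.

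The cost is wording in Sections 4.1, 4.2, 7.1, 8.2, 10.1 and the synopsis, one recorded history item and one table. No procedure, dose or sample size changes. A few patients become ineligible. The subgroup estimates will be imprecise: as an illustration, 3 responders among 15 would have an exact 95% interval of about 4% to 48%.

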7. Adequate organ and marrow function as defined below:
 - a. Absolute neutrophil count $\geq 1,000/\text{mm}^3$ without growth factor use ≤ 7 days prior to treatment (cycle 1 day 1, C1D1)
 - b. Platelets $\geq 50,000/\text{mm}^3$ without platelet transfusion ≤ 3 days prior to C1D1
 - c. Hemoglobin ≥ 8.0 mg/dL without red blood cell transfusion ≤ 3 days prior to C1D1
 - d. Total serum bilirubin $\leq 1.5 \times$ upper limit of normal (ULN); subjects with $>1.5 \times$ upper limit of normal require approval of medical monitor.
 - e. AST (SGOT)/ALT (SGPT) $\leq 2 \times$ ULN; $\leq 5 \times$ ULN if there is liver involvement secondary to tumor
 - f. Serum creatinine $\leq 1.5 \times$ ULN (OR creatinine clearance ≥ 30 mL/min/1.73 m²)
 - g. Serum or urine pregnancy test (for females of childbearing potential) negative ≤ 7 days of starting treatment
8. Ability to understand and the willingness to sign a written informed consent document and comply with the study scheduled visits, treatment plans, laboratory tests and other procedures.
9. Female patients must be surgically sterile or be postmenopausal, or must agree to use effective contraception during the period of the trial and for at least 90 days after completion of treatment. Male patients must be surgically sterile or must agree to use effective contraception during the period of the trial and for at least 90 days after

completion of treatment. The decision of effective contraception will be based on the judgment of the principal investigator or a designated associate.

Exclusion

1. Active inflammatory gastrointestinal disease, chronic diarrhea (unless related to underlying malignancy or prior related treatment) or history of abdominal fistula, gastrointestinal perforation, peptic ulcer disease, or intra-abdominal abscess within 6 months prior to study enrollment. Gastroesophageal reflux disease under treatment with proton pump inhibitors is allowed.
2. Pregnancy or breast feeding.
3. Current active treatment in another clinical study.
4. Active bacterial, fungal or viral infection including hepatitis B (HBV), hepatitis C (HCV)
5. Known human immunodeficiency virus (HIV) or acquired immunodeficiency syndrome (AIDS)-related illness that is not well controlled.
6. Active or prior plasma cell leukemia (defined as either 20% of peripheral WBC comprised of plasma/CD138+ cells or an absolute count of $2 \times 10^9/L$).

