4.2 Exclusion

1. Active inflammatory gastrointestinal disease such as chronic diarrhea (unless related to underlying malignancy or prior related treatment) or history of abdominal fistula, gastrointestinal perforation, peptic ulcer disease, or intra-abdominal abscess within 6 months prior to study enrollment. Gastroesophageal reflux disease under treatment with proton pump inhibitors is allowed.
2. Pregnancy or breast feeding
3. Current active treatment in another clinical study
4. Active bacterial, fungal or viral infection including hepatitis B (HBV), hepatitis C (HCV)
5. Known human immunodeficiency virus (HIV) or acquired immunodeficiency syndrome (AIDS)-related illness that is not well controlled.
6. Active or prior plasma cell leukemia (defined as either 20% of peripheral WBC comprised of plasma/CD138+ cells or an absolute count of $2 \times 10^9/L$)
7. Solitary bone or solitary extramedullary plasmacytoma as the only evidence of plasma cell dyscrasia.
8. Subjects with serum calcium (corrected for albumin) $\geq 12 \text{ mg/dL}$
9. Any of the following in the previous 6 months: myocardial infarction, severe/unstable angina, coronary/peripheral artery bypass graft, symptomatic congestive heart failure, cerebrovascular accident, transient ischemic attack or symptomatic pulmonary embolism.
10. Other severe acute or chronic medical or psychiatric condition or laboratory abnormality that may increase the risk associated with study participation or study drug administration, or may interfere with the interpretation of study results, or in the judgment of the investigator would make the patient inappropriate for entry into the study.
11. Actively receiving medications that have risk of Torsades de Pointes or are strong cytochrome P450 inhibitors or inducers.

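### The hemoglobin floor is printed as 8.0 mg/dL, which screens out nobody, and the synopsis and Section 4 word the AST/ALT exception and the chronic-diarrhea exclusion differently

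*Combined protocol and SAP*

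**What the plan says.** Eligibility is set out twice, in the Protocol Synopsis and in Section 4. Three items matter here.

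- **Hemoglobin (synopsis 7c, Section 4.1 7j).** Both lists print the same text: "Hemoglobin ≥ 8.0 mg/dL without red blood cell transfusion ≤ 3 days prior to C1D1".
- **AST/ALT (synopsis 7e, Section 4.1 7l).** Both set a limit of 2 times ULN and allow up to 5 times ULN under a condition. In the synopsis the condition is "if there is liver involvement secondary to tumor"; in Section 4.1 it is "if liver dysfunction is felt to be secondary to tumor burden".
- **Gastrointestinal exclusion 1.** The synopsis begins "Active inflammatory gastrointestinal disease, chronic diarrhea (unless related to underlying malignancy or prior related treatment", with chronic diarrhea as a separate item in a list. Section 4.2 begins "Active inflammatory gastrointestinal disease such as chronic diarrhea", with chronic diarrhea as an example of the inflammatory condition. The exception for diarrhea due to the malignancy or prior related treatment is the same in both.

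The only precedence rule is in Section 7, which ranks the Schedule of Activities above the text of that section. It does not cover eligibility.

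**The concern.** These are operative entry criteria. Section 7.1 allows enrollment once eligibility is confirmed, and Section 11 has monitors check CRF data against source documents. A threshold that no patient can fail gives neither step anything to check: a severely anemic patient who had not been transfused in the preceding 3 days would meet 7j as printed, and enrolling that patient would not breach its numeric limit.

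The other two items raise a different problem. The title page names investigators at two centers. If one works from the synopsis and the other from Section 4, they can reach opposite decisions on the same patient while each follows the protocol.

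What is at stake is who enters, whether entry can be verified, and, for AST/ALT, the baseline against which liver toxicity is judged in Phase 1.

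**Working it through.** **Hemoglobin.** Inputs: the printed floor of 8.0 mg/dL (both lists) and the other concentrations in the same list, namely the serum M protein floor ("Measurable disease M protein component in serum (at least 0.5 g/dL") and the free light chain threshold of 10 mg/dL, both in inclusion 2.

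- Conversion: 8.0 mg/dL ÷ 1,000 = 0.008 g/dL.
- M protein floor: 0.5 g/dL × 1,000 = 500 mg/dL, and 500 ÷ 8.0 = 62.5. The printed hemoglobin floor is 62.5 times lower than the M protein floor, and also below the 10 mg/dL light chain threshold.
- The documents give no hemoglobin distribution. Assume values from 3 to 15 g/dL: 3,000 ÷ 8.0 = 375 and 15,000 ÷ 8.0 = 1,875. Every value in that range is 375 to 1,875 times the printed floor.
- If g/dL was meant (an assumption for the sponsor to confirm), the floor is 8,000 mg/dL, and 8,000 ÷ 8.0 = 1,000 times the printed value.

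The unit is the same in both lists, so this is one error made twice and not a disagreement between them.

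**AST/ALT above 2 and up to 5 times ULN.** Each list applied to the four possible combinations:

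| Tumor involves liver | Dysfunction attributed to tumor burden | Synopsis 7e | Section 4.1 7l |
|---|---|---|---|
| Yes | Yes | Meets | Meets |
| No | Yes | Fails | Meets |
| Yes | No | Meets | Fails |
| No | No | Fails | Fails |

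The lists give opposite answers in two of the four rows.

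**Chronic diarrhea.**

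| Type | Synopsis exclusion 1 | Section 4.2 exclusion 1 |
|---|---|---|
| Due to malignancy or prior related treatment | Exception applies | Exception applies |
| Otherwise, inflammatory | Excluded | Excluded |
| Otherwise, non-inflammatory | Excluded | Not clearly excluded |

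The difference is confined to the last row.

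**Route to Phase 1 decisions (Sections 3.3, 5.6, 10.3).**

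- Anemia is not among the listed hematologic DLTs, and the general Grade 3 or higher rule covers only toxicity outside the blood and bone marrow class.
- Diarrhea is excepted from the Grade 3 or higher rule.
- Either can become a DLT only through the clause on events that prevent completion of planned study drug in the DLT window.
- Raised transaminases fall directly under the Grade 3 or higher rule.
- All of these need to be considered possibly related to ONC201, and Section 10.3 counts only discontinuations for treatment-related events.
- De-escalation requires more than 1 in 6 patients with a DLT. One in six is 1/6 = 17%, which equals the limit and does not exceed it; two are needed (2/6 = 33%).

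**Design figures.** The stated 84% power in Section 8.2 is reproduced with 30 patients and at least 7 responses: power 0.840 at a true rate of 30%, one-sided alpha 0.026 at 10%. None of the three criteria enters that calculation.

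**The case against.** The best reply is that this is editorial. Any site would read the hemoglobin floor as g/dL. Anemia is in any case not unrestricted: a patient transfused within 3 days of first dosing is still excluded, and exclusion 10 bars laboratory abnormalities that may raise the risk of participation. Both lists name chronic diarrhea with the same exception, and most readers of either would exclude an unexplained case. The synopsis does not say that liver involvement must be documented or that a lesion must be shown, so the AST/ALT contrast should not be drawn more sharply than the text draws it.

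Much of this stands. The practical effect of the hemoglobin unit is probably small, and the diarrhea difference is narrow. What does not stand is that the text can therefore be left alone. Exclusion 10 is largely a matter of judgment and does not give uniform entry. Inclusion 4, which requires acute effects of prior therapy to have resolved to baseline severity or Grade 1 or below, exempts parameters defined in the eligibility list, so it is not a clear backstop for hemoglobin. The two AST/ALT conditions remain different: one concerns the site of disease, the other a judgment of cause.

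A reader might go further and infer that loosely admitted patients will add baseline-driven DLTs, or that one such patient in a six-patient cohort would force de-escalation. The documents do not support this. Anemia and diarrhea have only the indirect route through inability to complete dosing. Attribution is required for DLTs and for the Section 10.3 counts. Section 8.1 records baseline signs and symptoms as adverse events only if they worsen or become more frequent. One DLT in six does not meet the trigger.

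**Conclusion.** The point holds as a defect in the written eligibility criteria. The numeric hemoglobin floor is non-binding as printed, by a factor of 1,000 if g/dL was meant. For AST/ALT above 2 and up to 5 times ULN, the two lists can give opposite decisions on the same patient. For chronic non-inflammatory diarrhea outside the shared exception, one list excludes and the other does not clearly do so. No statement settles which list governs.

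The consequence is inconsistent or unauditable entry, with a possible safety gap. Only AST/ALT has a direct Grade 3 or higher route to a DLT, and that is subject to attribution. Sample size, power and alpha do not change. The number of patients affected cannot be estimated, because the documents give no baseline distribution for any of the three measures. The conclusion that the floor excludes nobody rests only on patient hemoglobin being measured in whole grams per dL; that g/dL was the intended unit is an inference. The correction should be made, but it does not call the design into question.

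**What to change.** - Have the sponsor confirm the hemoglobin unit (apparently g/dL) and correct it in synopsis 7c and Section 4.1 7j.
- Reconcile the AST/ALT condition into one wording, used identically in synopsis 7e and Section 4.1 7l. Which clinical condition applies is for the sponsor to decide.
- Reconcile exclusion 1 into one wording in the synopsis and Section 4.2 that states plainly whether chronic diarrhea alone excludes. That choice is also the sponsor's.
- Carry the final text to the eligibility checklist.

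Once the two lists are identical, no precedence statement is needed for these items. The cost is wording in two lists and on the checklist, with the amendment approval that any such change needs. It requires no additional patients, visits or procedures.
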